Duration of Participant Intake (Study Duration) The CS #2003 study duration is projected to be a total of seven years: The initial six sites will have a start-up year, followed by participant enrollment/data collection during years 1-4, and continued data collection/closeout during year 5, for a total of six years. The next four sites will begin the start-up year one year after the first six sites and follow the same enrollment, data collection and closeout schedule over the next five years. The next five sites will begin start-up one year after the four sites and follow the same enrollment, data collection and closeout schedule. All fifteen sites will be closed out after six years, and there is an additional year for the Coordinating Center and Chairperson's Office to complete data analysis and manuscript writing, thus the study total time is seven years. Participants in both groups will be asked to commit 33 weeks to this study. Participants in the Control arm will be offered an additional 8 weeks to receive EAW training in the medical centers, without outcome data being collected.

Treatment (follow-up) The intervention being tested is four months of home and/or community use of a powered exoskeleton.

Definition of Participant Samples (Study Population) One-hundred sixty male or female Veterans or military members with chronic SCI, \geq six months duration, \geq 18 years of age, functional use of their hands, medically stable, and wheelchair users for indoor and outdoor mobility, will be eligible for screening. All potential participants will be Veterans or military members with SCI. Study participants will generally be outpatients with the exception of those inpatients who meet the eligibility criteria, and who are approved by the Site Investigator (e.g., some inpatients may have been admitted for a wheelchair fitting or another non-medical reason). Non-veterans with SCI will not be eligible.

Treatment Arms All participants will receive four months of treatment, randomized into two arms: SOC plus EAW or SOC only.

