In order to avoid potential participants not being interested in the study because of the 50% chance of not receiving the intervention, the Control group will be offered a two-month EAW training program after completion of the study protocol as an outpatient. Outcome data will not be collected during this outpatient, EAW post-study training for the Control group. The study site team will provide the EAW training to the former Control group participants during this phase and adverse events will be recorded during this post study component for the Control group. After participation in the study, participants may be considered for home use prescription of the exoskeleton by the clinical SCI Service.

D. Study Duration and Timeline

CS #2003 is projected to be a seven-year study. A staggered start approach will be employed with six sites starting during the first year of the study, four sites starting one year later, and five sites starting two years later. The six sites will have a one-year start-up, four years of enrollment and an additional one year of data collection and study closeout. The four sites will follow the same plan, but starting one year later with three years of enrollment. The remaining five sites will start two years later and have two years of enrollment and one year of data collection and closeout. All 15 sites will complete data collection and study closeout in the sixth year of the study. An additional year for the Coordinating Center and Chair's Office is planned for data analyses and write-up (seven years in total). During the 6-week pre-start-up period, the Chair's Office will begin staff hiring procedures by providing position description (PD) postings for the sites, and submit the protocol to the Central Institutional Review Board (CIRB) and local Research & Development (R&D) for review. The CSPCRPCC will submit the investigational device exemption (IDE) application to the FDA. A year will be needed for study start-up activities for the sites CIRB and local R&D submissions, ordering of the equipment (ReWalks and iDXA scanners), site staff hiring, and the ReWalk and study protocol training. During the enrollment years 1-4, participants will be prescreened, screened, and randomized. Year five will be used for continuation of data collection; no new enrollment will occur in year six. Data edits will be ongoing throughout the five years of data collection. Year six will be needed for general wrap-up and

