Chair/Sites' R&D	x	x																														
Chair's funding received		x	x																													
Chair/Sites' staff hiring		x				x								x																		
Sites' CIRB		x	x																													
Equipment contracts		x	x																													
Equipment ships to sites			x	x										x																		
iDXA Site training			x	x	x		x	x						x	x																	
ReWalk onsite training ¹			x	x	x		x	x						x	x																	
ReWalk training follow-up ²				x		x	x		x	x		x	x		x	x		x	x													
Study meetings			x				x			x			x			x			x			x										
Pre Screening			x	x		x	x	x	x		x	x	x	x		x	x	x	x		x	x	x	x								
Screening				x		x	x	x	x		x	x	x	x		x	x	x	x													
Randomization						x	x	x	x		x	x	x	x		x	x	x	x													
Data collection/edits						x	x	x	x		x	x	x	x		x	x	x	x		x	x										
Study close out																																
Data analyses/writing																																

Table 5 Legend. A total of 160 (80/group) participants will be enrolled and randomized across all 15 study sites. CIRB=Central Institutional Review Board (VA); CSPCRPCC =Cooperative Studies Program Clinical Research Pharmacy Coordinating Center; IDE=Investigational Device Exemption; FDA=Food and Drug Administration; PD=Position descriptions for hiring staff; R&D=Research and Development Committee (at Sites and Chair's Office); iDXA=DXA scanner for bone mineral density and total body composition. ¹ReWalk Site training is performed by ReWalk Robotics, Inc. as onsite training. ²ReWalk Site training follow-up is performed by the CS #2003 National Coordinator as a follow-up training at the sites.

Table 6. Testing and Training Schedules

Phases:	Screening Phase		Orientation/Training Phase		Intervention Phase				Control EAW			
	Month 1		Mo 2 to 4		Mo 5	Mo 6	Mo 7	Mo 8	Mo 9	Mo 9 & 10		
	1 to 4		5 to 16		17 to 20	21 to 24	25 to 28	29 to 32	33	33 to 40		
Pre Screening	Consent Obtained	Screening Evaluations	Orientation/Training		In-Home/Community				Post Intervention Phase Evaluations (Both Groups)	(no Data)		
			Control Group (Standard of Care Review)	Orientation/Training Phase Evaluations (Both Groups)	Control Group (Standard of Care)							
			Intervention Group (EAW Training)			Intervention Group (Standard of Care plus Home EAW)						
SCREENING Evaluations		Pre Evaluations (Baseline for both groups)								Control Group; No study data collection (EAW In-hospital training, 3x/week for 2 months)		
History & Physical Exam			x									

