D. The **VA Central IRB (CIRB)** will be the study's primary IRB and the IRB of record for the study. It will be responsible for the initial and continuing IRB reviews of the study. The CIRB must review and approve amendments (changes to inclusion/exclusion criteria, protocols, informed consents, etc), deviations, and review reports about adverse events and problems, complaints, terminations, etc.. The CIRB approves the original informed consent template and any requested changes to the informed consent forms. The CSPCC Human Rights Committee (HRC) may be asked to convene if there is any serious adverse event requiring its attention.

E. Definitions of Adverse Event (AE), Serious Adverse Event (SAE), and Unanticipated Adverse Device Effect (UADE)

An Adverse Event (AE) is defined by the International Conference on Harmonization (ICH) for Clinical Safety Data Management (ICH-E2A) as “any untoward medical occurrence in a clinical investigation participant that is subjected to one of the study treatments that does not necessarily have to have a causal relationship with the treatments. An AE, therefore, can be any unfavorable or unintended sign (including an abnormal laboratory finding), symptom, or disease temporally associated with the study interventions.” In this study, all AEs will be collected by the Sponsor. The reporting period for AEs begins when the participant signs the informed consent form and continues until the participant’s completion or early termination of participation or the end of the study.

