A Serious Adverse Event (SAE) is defined by the ICH for Clinical Safety Data Management and CSP Global SOP 3.6.2, as any untoward medical occurrence that: results in death, is life threatening, requires inpatient hospitalization or prolongation of existing hospitalization, results in persistent or significant disability or incapacity, a congenital anomaly/birth defect, or any other condition that, based upon medical judgment, may jeopardize the subject and require medical, surgical, behavioral, social or other intervention to prevent such an outcome. Participants will be monitored for SAEs at each study visit. All SAEs will be reported on an SAE Form, regardless of relationship to the intervention. Active monitoring for SAEs begins at the time the Informed Consent Form is signed and continues until the earlier of the 30 days after the participant’s completion or early termination of study participation or the end of the study. All SAEs require prompt reporting to the CSP Clinical Research Pharmacy Coordinating Center (CSPCRPCC) within 72 hours of the Site Investigator becoming aware of the event. All **unresolved** SAEs must be followed up at least every 30 days until resolved or when no further change is expected (i.e. event is ongoing recovering/resolving or not recovered/not resolved. No changes to the event will occur in the future.) All SAEs are followed until no changes are expected or the study is discontinued.

An unanticipated adverse device effect (UADE) is defined in 21 CFR 812.3(s) as any serious adverse effect on health or safety or any life-threatening problem or death caused by, or associated with, a device, if that effect, problem, or death was not previously identified in nature, severity, or degree of incidence in the investigational plan or application (including a supplementary plan or

application), or any other unanticipated serious problem associated with a device that relates to the rights, safety, or welfare of subjects

Starting with each site, at the local level, the site study team members will be responsible for recording adverse and serious adverse events, as well as unanticipated adverse device effects and submitting them to the appropriate authorities in the time frames listed below.

F. Serious Adverse Event (SAE) Reporting

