Any Serious Adverse Event (SAE) is reported on both the SAE and AE case report forms. The Site Investigator will be responsible for reporting a SAE, ascertaining the participant's study identification number, date of event, and will determine if the SAE is related, possibly related or not related to the protocol. A description of any outcome or response to the SAE will also be included in this report. As more information about a SAE becomes available, updates to this initial report must be made on the SAE Follow-Up form. It is the responsibility of each Site Investigator to report SAEs from their site to the CIRB within the timelines they require. SAE data are tabulated by the CSPCC at [name] and the CSPCRPCC at Albuquerque, NM, and summarized and in the report to the DMC. ReWalk Robotics, Inc. will be provided a summary of SAEs annually.

G. Adverse Event (AE) and Unanticipated Adverse Device Effect (UADE) Reporting

Any mild (awareness of symptom, but easily tolerated), moderate (discomfort enough to cause interference with usual activity) or severe (incapacitating with inability to work or do usual activity) AE must be reported on the AE case report form. Any AE which also meets the criteria for a SAE must also be reported on the SAE form. It is the responsibility of each Site Investigator to report AEs from their site annually to the CIRB. Participants will be monitored at a minimum of one time per week for AEs and recorded on the appropriate form should any occur. AE data are tabulated by the CSPCC at [name] and the CSPCRPCC at Albuquerque, NM and summarized in the report to the DMC.

UADEs must be reported by the clinical investigator to the sponsor and the CIRB, Investigators are required to submit a report of a UADE to the sponsor and the reviewing IRB as soon as possible, but in no event later than 10 working days to the sponsor and no later than 5 days to the CIRB after the investigator first learns of the event. This reporting will be to the CSP Clinical Research Pharmacy

Coordinating Center on an AE or SAE form, as appropriate, and to the CIRB on the relevant IRB form. The reporting period for UADEs begins when the participant signs the informed consent form and continues until the participant's completion or early termination of participation or the end of the study

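### The UADE reporting period ends up to 30 days before SAE monitoring, and the safety-reporting rules for the Control group's post-study exoskeleton training contradict each other

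*Combined protocol and SAP*

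**What the plan says.** - **AEs (XI.E).** Reporting opens at consent and closes at "completion or early termination of participation or the end of the study".
- **UADEs (XI.G).** The same end point, in the same words. Reports are due within 10 working days to the sponsor and 5 days to the central IRB (CIRB).
- **UADE definition (XI.E).** It covers "any serious adverse effect on health or safety or any life-threatening problem or death caused by, or associated with, a device", provided that the effect had not already been identified in nature, severity or incidence. It also covers other unanticipated serious device problems.
- **SAEs (XI.E).** Active monitoring "continues until the earlier of the 30 days after the" participant's completion or early termination, or the end of the study. A separate sentence requires every SAE to reach the pharmacy coordinating center (CSPCRPCC) within 72 hours of the Site Investigator learning of it. That sentence has no end date.
- **Control training.** III.C: "the Control group will be offered a two-month EAW training program after completion of the study protocol as an outpatient". The same section adds that "adverse events will be recorded during this post study component for the Control group". The Executive Summary, after a 33-week commitment for both groups, says: "Participants in the Control arm will be offered an additional 8 weeks to receive EAW training in the medical centers". Table 6 puts this in weeks 33 to 40 ("EAW In-hospital training, 3x/week for 2 months") and labels the column as one in which no study data are collected.

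Section XI does not define completion for safety reporting, does not mention the post-study training, and does not refer to III.C.

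**The concern.** There are two separate problems.

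First, the most serious class of device event has a shorter reporting period than serious events in general. This applies to every participant in both groups.

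Second, the optional training is the main device exposure for a Control participant who takes it: 3 sessions a week for 8 weeks, or 24 sessions, against 5 basic sessions before randomization. Study staff deliver it. A site reading III.C would record AEs. A site reading XI.E, XI.G and Table 6 could conclude that AE and UADE reporting had ended. Both could claim to have followed the protocol.

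Device safety is a stated aim in section II, so the question of which events must be reported, to whom and by when should not depend on which section a site consults.

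**Working it through.** The plan gives no figure for this point. The check is a comparison of texts followed by a count of days.

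**1. UADE period against SAE period**

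| | Ends | Stated deadline |
|---|---|---|
| SAE | 30 days after completion or early termination, or end of study if earlier (active monitoring) | 72 hours to CSPCRPCC; CIRB on its own timelines |
| UADE | completion or early termination, or end of study | 10 working days to sponsor; 5 days to CIRB |

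Taking the first of the listed events as the end of the UADE period, the difference is up to 30 days, wherever completion is placed. An unanticipated serious device effect found in that interval is an SAE and goes to the CSPCRPCC within 72 hours. It is outside the stated UADE period, and so outside the 5-day CIRB deadline.

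**2. Where completion falls**

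*Before the optional training (main reading).* III.C is headed as post-study participation, places the training after the protocol is completed, and calls its recipients former Control participants. The Executive Summary counts the 8 weeks on top of the 33. III.D says that the training follows the end of the study. XIII.F defines completers by the end of the four-month intervention phase.

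*After the optional training (alternative reading).* III.D also gives Control participants seven to nine months to complete the study and attributes the extra time to this training. Its own breakdown agrees: 1 month of screening + 2 months of orientation + 4 months of intervention = 7, and 7 + 2 months of training = 9 (leaving aside one week of post evaluations). The Table 6 legend also allows the exit survey after the training.

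**3. Days of Control training covered**

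Training length: weeks 33 to 40 inclusive = 40 − 33 + 1 = 8 weeks = 8 × 7 = 56 days, which agrees with the 8 weeks in the Executive Summary.

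On the main reading, the AE and UADE periods cover 0 of 56 days. For active SAE monitoring, counting days from completion:

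uncovered days = end of training − the later of (day 30, start of training)

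| Case | Uncovered by active SAE monitoring |
|---|---|
| Starts at once, 56 days | 56 − 30 = 26 of 56 (46%) |
| Completion at end of week 33, so 7 weeks remain | 49 − 30 = 19 of 49 |
| Two calendar months, 61 days | 61 − 30 = 31 of 61 |
| Starts 14 days later (assumed) | 70 − 30 = 40 of 56 |
| Starts 30 days later (assumed) | 86 − 30 = 56 of 56 |

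So for a 56-day course, active SAE monitoring covers at most 30 days.

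On the alternative reading, all three periods cover the whole training and no days are uncovered. The difference in step 1 remains.

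**The case against.** The best defence is that III.C addresses this exact period and commits the study to recording AEs. XI.G then says that an AE meeting the SAE criteria must also go on the SAE form, and UADEs use the AE or SAE form. A specific provision can fairly be read as extending the general one. This stands to the extent that AEs in Control training are meant to be captured. It does not settle the matter: III.C speaks only of recording, sets no SAE or UADE deadline or recipient, and conflicts with the AE and UADE end points and with the Table 6 label. That label may have been meant for outcome data only, as in III.C, but it does not say so.

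The AE and UADE sentences also lack the words that make the SAE limit the earlier of two dates, so the end of the study might be said to govern. That is a weak reading, because naming the participant's completion would then serve no purpose.

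The 30-day difference has limited practical effect. The event still reaches the same CSPCRPCC, and sooner than the UADE limit requires. What may be lost is the UADE classification and the 5-day CIRB deadline.

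Three stronger inferences are not supported:

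- *That a serious event late in Control training would trigger no 72-hour report.* The 30-day limit attaches to active monitoring. The 72-hour rule has no stated end, and the staff giving the training would learn of the event.
- *That an unnoticed fracture shows what would be missed.* XVIII.F lists fracture as a foreseeable risk, so it would not ordinarily meet the UADE definition. The wording on unnoticed fractures in section VIII belongs to the exclusion criteria.
- *That a given share of the trial's device exposure goes unreported.* The documents give no uptake for the optional training, and a share based on supervised sessions would leave out the Intervention group's four months of home use.

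**Conclusion.** The point holds as a defect in the reporting rules. The UADE period is up to 30 days shorter than the SAE period for all participants, although a UADE is serious by definition. This does not depend on where completion is placed.

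For the Control group's optional training, the protocol gives contradictory instructions. On the reading that most of the text favours, the AE and UADE periods cover none of the 56 days and active SAE monitoring covers at most 30. On the reading that III.D also allows, everything is covered. The size of the gap therefore rests on an undefined word, on when training starts, and on how many Control participants accept it. The documents show unsettled duties, not events that are certain to be lost.

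It is a cheap safety-reporting correction and worth making. No endpoint, sample size, power or significance level is affected.

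**What to change.** Reconcile III.C, III.D and Table 6 with XI.E to XI.G:

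1. Define completion for safety reporting, separately from the definition of completers in XIII.F.
2. State that, for Control participants who take the optional training, AE, SAE and UADE reporting applies through the last session plus the same 30-day follow-up.
3. For all participants, make the UADE period at least as long as the SAE period, and say explicitly which of the listed events ends each period.
4. Cross-refer to these rules from III.C and Table 6, and limit the Table 6 label to outcome data.

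The cost is protocol wording and a few more AE, SAE and UADE forms. Study staff already run these sessions, and III.C already intends AE recording.
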